6.2 Data Security

Describe the steps that will be taken to secure the data (e.g., training, authorization of access, password protection, encryption, physical controls, certificates of confidentiality, and separation of identifiers and data) during storage, use, and transmission.

As noted above, to assure confidentiality, anonymous data and recordings of therapy sessions will be secured in a database management system, password protected files, and in secure file cabinets. Data collection forms, databases, and recordings will not include identifiers other than a study ID code. We will include all three levels of security: password protection, computer or file cabinet locks, and a locked office. Participants' encrypted cognitive task data will be housed on a secure server "using Secure Sockets Layer (SSL), the same technology used by online shopping and banking web sites to protect sensitive information transmitted over the web"

6.3 Data and Safety Monitoring

A. Periodic Data Evaluation

Describe the plan to periodically evaluate the data collected regarding both harms and benefits to determine whether subjects remain safe. The plan might include establishing a data monitoring committee and a plan for reporting data monitoring committee findings to the IRB and the sponsor.

The Data and Safety Monitoring Board (DSMB) will meet every 3 months to monitor and evaluate the safety of participants throughout the course of the research study. The DSMB will:

- Assess the performance of the study with respect to participant recruitment, retention and follow-up, protocol adherence, and data quality and completeness.
- Monitor interim data regarding the safety of the study regimes.
- Review and consider any protocol modifications or ancillary studies proposed by study investigators after the main trial begins to ensure that these do not negatively impact on the main trial.
- Advise the Institutional Review Board as to whether the protocol should continue as scheduled or undergo a modification due to a finding from the monitoring process.

B. Type of Data Evaluated

Include what data are reviewed, including safety data, untoward events, and efficacy data.

The study investigators and the DSMB will be responsible for data safety and monitoring. Quarterly, the DSMB and the investigators will monitor the cumulative safety data during the period when participants are in the study. They will: 1) assess the performance of the study with respect to participant recruitment, retention and follow-up, protocol adherence, and data quality and completeness, to help ensure the likelihood of successful and timely trial completion; 2) monitor interim data regarding the safety of the study regimens; 3) review and consider any protocol modifications by the study investigators after the trial begins to ensure that these do not negatively impact on the study; and 4) advise the Institutional Review Board and NIH as to whether the protocol should continue as scheduled or undergo a modification due to a finding from the monitoring process.

C. Collection of Safety Information

Explain how the safety information will be collected (e.g., with case report forms, at study visits, by telephone calls with participants).

Safety information will be collected during participant's assessments, telephone calls with participants, conversations with clinic staff, and MORE group sessions.

D. Frequency of Data Collection

The frequency of data collection, including when safety data collection starts.

Safety data collection will begin with collection of the first baseline assessment and continue through the end of the follow-up data collection period (12 months total). In addition to using assessment data to monitor safety, study clinicians will record any adverse events that they become aware of during MORE group sessions and study Investigators will ask NBCC and the Lennard Clinic personnel, with participant consent, to notify the research team should they become aware that any study participant has been hospitalized or experienced any other adverse event. Such notifications will be requested throughout the study period. All adverse events will be recorded on spreadsheets and will include details of the adverse event and whether or not it was study-related. Numbers and types of events and other quantifiable event details will be entered into a database for analysis.

E. Reviewer of Data

Who will review the data?

The DSMB will meet on a quarterly basis to monitor the cumulative safety data during the period when participants are in the study. The DSMB will monitor the study according to the guidelines specified in the study protocol and the operating procedures established at the initial DSMB meeting, unless the DSMB determines during the course of the trial that modification of the guidelines is in the best interest of the study and its participants. Such a decision may be based on new information that emerges during the course of the study (e.g., publication of the results of a similar study), realization of inappropriate initial study assumptions, or the occurrence of an unanticipated scenario.

F. Schedule of Review of Cumulative Data

The frequency or periodicity of review of cumulative data.

Under supervision of the investigators, the Research Assistant will conduct monthly descriptive summaries on all data to ensure their accuracy. This will not involve completing any statistical comparisons. If problems are noted in data entry (e.g., out of range values, missing values), the Research Assistant and the investigators will investigate the root cause, and solutions to rectify the problem.

G. Tests for Safety Data

The statistical tests for analyzing the safety data to determine whether harm is occurring.

Basic statistical tests, including frequency distributions, Anovas and t-tests, will be carried out to compare the control and intervention groups on numbers and types of adverse events within specific time frames in order to insure the safety of the intervention.

H. Suspension of Research

Any conditions that trigger an immediate suspension of the research.

Considering the minimal risk nature of the intervention, we do not anticipate any serious adverse events that could trigger the immediate suspension of the research.

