1.3 Research Design and Methods

This pilot study is a 2-arm individually randomized controlled trial design in which outcomes of MMT patients randomized to MORE are compared to outcomes of those randomized to treatment as usual (TAU). In the pilot study (R21; N=31), we will randomize MMT patients with chronic pain to MORE (n=15) or TAU (n=16). This study phase will focus on establishing study feasibility in recruiting, retaining, and following up study participants before progressing to a larger Phase II clinical trial (R33, N=150). Participants with pain who are receiving MMT for an opioid use disorder (OUD) will be recruited from the New Brunswick Counseling Center (NBCC) and the Lennard Clinic.

A. *Describe, in order of occurrence, all research procedures being performed, when and where they are performed, and by whom (including procedures being performed to monitor subjects for safety or minimize risks).*

Participants will be recruited through flyers posted in the clinics, being approached by research assistants in the waiting room of their usual methadone clinic (New Brunswick Counseling Center or Lennard Clinic), and referral by clinic staff. The number of individuals who contact the study staff through the flyers or referral and who are approached by study staff in the clinics will be tracked. Number of individuals who refuse study participation and who consent to the study will also be tracked. If an individual is interested in study participation, a trained research assistant will lead the individual through the informed consent process in a private space.

Participants randomized to the MORE condition will participate in eight, weekly, two-hour group sessions led by a clinic or study counselor. Each session will contain 4-8 participants and take place in a private room at the New Brunswick Counseling Center (NBCC) or the Lennard Clinic. Attendance at each session and reasons for missing sessions will be recorded. Participants randomized to the control condition will continue receiving treatment as usual at the NBCC.

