All study participants will partake in a total of three interviews lasting up to 90 minutes and occurring at baseline, 8- and 16- weeks post-baseline in a private room at NBCC or the Lennard Clinic. Each participant will also have a urine or saliva sample collected during each assessment. This is required to verify self-report of drug use. Due to social desirability, it is common for people to not accurately report drug use; therefore, biochemical verification is the gold standard measure of drug use. All attempts to reach participants to schedule follow-up assessments will be tracked. Participants will also complete cognitive testing (for approx. 30-45 minutes) at baseline and 8-weeks and ecological momentary assessments (EMA) conducted via smartphones, which will be provided to each participant by study staff. EMA participation will require the participant to respond to twice-daily prompts in which they will be asked a series of brief questions regarding their current mood and exposure to opioid triggers. Additionally, subjects will be asked to initiate responses when they experience serious craving or relapse to opioid use. Each EMA assessment will last approximately 3-5 minutes.

B. What data points will be collected including long-term follow-up?

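### Adverse events heard in MORE sessions are a detection source in one arm only, yet they enter the between-arm safety comparison and bias it toward MORE looking less safe

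*Combined protocol and SAP*

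**What the plan says.** Section 6.3 C names four routes: "Safety information will be collected during participant's assessments, telephone calls with participants, conversations with clinic staff, and MORE group sessions". Section 6.3 D adds that "study clinicians will record any adverse events that they become aware of during MORE group sessions". It also says that clinic personnel will be asked, with participant consent, "to notify the research team should they become aware that any study participant has been hospitalized or experienced any other adverse event". Events are put on spreadsheets with their details and a judgement of study-relatedness, and the quantifiable details then go into a database. No field for the route of detection is mentioned.

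Section 6.3 G says that frequency distributions, ANOVAs and t-tests "will be carried out to compare the control and intervention groups on numbers and types of adverse events", within time frames that are not defined, to check that the intervention is safe.

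On contact, section 1.3 says: "Participants randomized to the MORE condition will participate in eight, weekly, two-hour group sessions led by a clinic or study counselor". For the other arm: "Participants randomized to the control condition will continue receiving treatment as usual at the NBCC". The research interviews are common to both: "All study participants will partake in a total of three interviews lasting up to 90 minutes", at baseline, 8 weeks and 16 weeks.

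**The concern.** Three of the four routes cover both arms, and the fourth covers only MORE. It is a working source. Section 4.9 A says that information about possible harm to self or others that comes up in intervention sessions can be acted on, and that a new or worsening finding of this kind counts as an adverse event.

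Because the events are pooled, a difference in counts mixes the true event rate with the chance of hearing about an event. An added source in one arm can only raise that arm's expected count. The between-arm comparison could therefore suggest harm where there is none, or mask a true reduction in events under MORE. A DSMB reading small counts each quarter, with no record of source, could not tell these apart. The pilot exists to test methods for a larger trial, so the same comparison could be carried forward.

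**Working it through.** **No figure to reproduce.** The documents give no adverse-event rate, no capture probability and no power for safety. What follows is an illustration under stated assumptions.

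**Inputs from the documents**
- Session route in MORE only: 6.3 C, 6.3 D and 1.3.
- Eight weekly sessions; 16 weeks of participation: 1.3.
- Arm sizes 15 (MORE) and 16 (TAU): 1.5.

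**Assumptions**
- Equal true event rates in the arms, with events spread evenly over 16 weeks.
- Shared sources catch a share *d* of events, the same in both arms.
- Sessions catch a share *e* of the events that shared sources miss, during the eight session weeks only, with full attendance.

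**Formulas for the expected MORE:TAU ratio of recorded events**
- Session weeks: [d + (1 − d)e] / d
- All 16 weeks, sessions covering half: [d + (1 − d)e/2] / d

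| d | e | Session weeks | 16 weeks |
|---|---|---|---|
| 0.5 | 0.25 | 0.625/0.5 = 1.25 | 0.5625/0.5 = 1.125 |
| 0.5 | 0.50 | 0.75/0.5 = 1.50 | 0.625/0.5 = 1.25 |
| 0.7 | 0.25 | 0.775/0.7 = 1.11 | 0.7375/0.7 = 1.05 |
| 0.7 | 0.50 | 0.85/0.7 = 1.21 | 0.775/0.7 = 1.11 |
| 0.9 | 0.25 | 0.925/0.9 = 1.03 | 0.9125/0.9 = 1.01 |
| 0.9 | 0.75 | 0.975/0.9 = 1.08 | 0.9375/0.9 = 1.04 |
| 1.0 | any | 1.00 | 1.00 |

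**Direction.** The excess over 1 is (1 − d)e/d, or half that over 16 weeks. It is never negative. It is zero only if d = 1 or e = 0.

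**Attendance.** If *e* falls in proportion to sessions attended, attending 4 of 8 halves it. The 16-week range for d = 0.5 to 0.7 becomes (0.7 + 0.3 × 0.125/2)/0.7 = 1.03 to (0.5 + 0.5 × 0.25/2)/0.5 = 1.13.

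**Effect on the planned test.** Event counts over 16 weeks were simulated as Poisson with 15 versus 16 participants, true rates of 1 or 2 events per person (assumed), a two-sided t-test at 0.05 and 20,000 replicates.
- With d from 0.5 to 0.7 and e from 0.25 to 0.50, MORE showed the higher mean in about 53% to 75% of replicates, and the test rejected in about 5% to 10%.
- With d = 0.9, e from 0.25 to 0.75, these were about 51% to 55% and 5%.
- With d = 1.0, they were about 49% to 50% and 5%.

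**After the change.** If the comparison uses only sources common to both arms, the session term drops out and the expected ratio is d/d = 1.00.

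**The case against.** The strongest case on the other side has four parts.

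**The shared sources may be strong.** Section 1.6 A describes clinic attendance of usually six days a week early in treatment, plus counseling, and clinic personnel are asked about every participant throughout. At 90% shared capture the bias almost disappears. This stands as a limit on size. It does not remove the bias, because MORE participants have the same clinic contact and the sessions come on top. Nor do the documents show that shared capture is near complete. The clinic route is passive and needs consent. Only two assessments follow baseline, and the follow-up benchmarks accept 65% and 50%, although the targets are 80% and 75%.

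**Contact hours are a poor guide.** A reader might infer a four-fold difference in detection from scheduled hours: 8 × 2 + 3 × 1.5 + 2 × (0.5 to 0.75) = 21.5 to 22 in MORE against 5.5 to 6 in TAU. The documents do not support that reading. It omits routine clinic contact and twice-daily EMA in both arms. EMA comes to 2 × 7 × 16 = 224 prompts of 3 to 5 minutes, or 11.2 to 18.7 hours. Adding it brings the ratio to (22 + 18.7)/(6 + 18.7) = 1.65 up to (21.5 + 11.2)/(5.5 + 11.2) = 1.96. Whether EMA feeds the safety data is not stated. Session time is also shared by groups of 4 to 8. Hours do not enter the ratios above.

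**Dropping session events has its own risk.** Section 4.9 A names discomfort in group sessions as part of the main risk, so excluding session-only events could hide harms that MORE causes. A column holding only the first source could also undercount MORE, if an event already heard in a session is not logged again at week 8. Both points stand and shape the fix.

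**The stakes are low.** This is an unpowered pilot of 31. The progression milestones in 1.1 B contain no safety criterion, and 6.3 G ties no stopping rule to the comparison. That limits the consequence, but low power does not remove bias.

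**Conclusion.** The concern holds as a bias in direction, with a size that the documents do not fix. Following the plan as written, equal true rates give an expected comparison that leans against MORE whenever shared sources miss events that the sessions reveal. No other section corrects this.

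On the assumptions shown, the expected ratio is 1.11 to 1.50 within the session weeks and 1.05 to 1.25 over 16 weeks. It is close to 1 if shared capture is high, and smaller again if attendance is incomplete. Because 6.3 G leaves its time frames open, a baseline-to-week-8 window would carry the larger figures.

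A reader might infer that MORE will look less safe. The documents do not support that certainty: both capture shares are assumptions, and with 15 against 16 participants chance or a true benefit could outweigh the bias. The change is worth making because it is cheap and the safety comparison may be reused in the larger trial. It is not a reason to doubt the pilot's feasibility aims.

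**What to change.** **In 6.3 D**
- Record every source through which each event was learned, not only the first. An event heard while leading a session counts as session-sourced even if the leader is a clinic counselor, since 1.3 allows either kind of leader.
- Ask the same adverse-event questions in both arms at the existing 8- and 16-week assessments, in person or by telephone. Log each event reported there even if it is already known from a session.

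**In 6.3 G**
- Base the between-arm comparison on events captured by sources common to both arms.
- Show the all-source comparison beside it.
- List session-only events separately with study-relatedness, so that harms arising from the sessions stay visible.

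Recording in sessions and all reporting to the DSMB and the IRB stay as they are.

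**Cost.** A few more fields on the adverse-event record, a few more questions at two existing visits, and slightly fewer events in the shared-source comparison. That comparison still assumes that the shared sources work equally well in both arms; the identical questions are what make this credible.

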MORE sessions. We will consider our ability to follow participants successful if we obtain 8-week assessments from at least 65% of participants and 16-week assessments from at least 50%. Although we are targeting a follow-up rate in both groups of at least 80% and 75% at 8 and 16 weeks, respectively, we set the benchmarks at 65% and 50% because, again, if necessary, we can adapt follow-up strategies for the next study, based on lessons learned in this study.

Preliminary outcome measures to be assessed during this pilot study will be time until opioid lapse and MMT dropout. Preliminary secondary outcomes will be: days of methadone medication use, days of opioid and other drug use, and changes in pain severity and intensity. Additional measures are described below.

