1.10 Timetable/Schedule of Events

Table 1. R21 Timeline		Year 1											
Month		1	2	3	4	5	6	7	8	9	10	11	12
Protocol manual writing and staff training													
Recruitment													
Intervention period													
Follow-up data collection													
Pilot study data analyses													
R33 protocol manual writing, institutional review board application and approval													
Recruit and hire R33 staff													

assessments will begin in month 6 and continue through month 9, and 16-week follow-ups will begin in month 8 and continue through month 11. In month 11, we will finalize our assessment of study feasibility. At the end of

The project timeline proposes to spend three months conducting start-up activities, with study recruitment beginning in month 4 and continuing through month 7. The intervention will begin in month 4 and continue through month 9, 8-week follow-up

month 11, we will prepare a report summarizing our feasibility findings for NCCIH and seek approval for continuing to a larger, fully powered, randomized controlled trial. Data collection for this pilot study will be 8 months.

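### The safety comparison in Section 6.3 G counts adverse events without allowing for time under observation, so the arm ratio can be distorted if retention differs between arms

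*Combined protocol and SAP*

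**What the plan says.** **Comparison.** Section 6.3 G states the only between-arm safety analysis, which is to "compare the control and intervention groups on numbers and types of adverse events within specific time frames". The methods it names are simple ones: tables of frequencies, analysis of variance and t-tests. It does not define the time frames, and does not say whether events or participants with an event are counted. It gives no rate, and no rule for someone lost during a frame. No other section supplies these.

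**Sources.** Section 6.3 C: "Safety information will be collected during participant's assessments, telephone calls with participants, conversations with clinic staff, and MORE group sessions". Section 6.3 D adds that "study clinicians will record any adverse events that they become aware of during MORE group sessions", a source that exists in one arm only. It also says that clinic personnel will be asked, with participant consent and for the whole study period, to "notify the research team should they become aware that any study participant has been hospitalized or experienced any other adverse event". Section 1.3 B offers a telephone interview when a visit is not attended.

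**Retention.** Section 1.3 calls follow-up successful if "we obtain 8-week assessments from at least 65% of participants and 16-week assessments from at least 50" per cent. The target is 80% and 75%, the same in both arms. Hypothesis 2 in Section 1.1 B expects longer time to methadone dropout with MORE.

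**Duration.** Section 6.3 D has safety collection start at the first baseline assessment and "continue through the end of the follow-up data collection period (12 months total". Section 1.10 says: "Data collection for this pilot study will be 8 months".

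**The concern.** A fixed time frame sets the calendar window, but not how much of it is observed for each person. Someone lost to both the study and the clinic contributes no further events and is still treated as event-free for the rest of the frame. If such loss differs between arms, the comparison mixes the event rate with the length of observation. An arm that keeps people longer can then appear to have more events. An arm that loses people can have real harms hidden.

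The comparison is meant to establish that the intervention is safe, and the pilot is meant to inform a larger trial of 150. Both the arm ratio and the absolute event rates would be carried forward.

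**Working it through.** The documents give no adverse event rate, no expected count and no level for the safety tests, so there is no figure of the plan's own to reproduce. What follows is a sensitivity illustration.

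**Inputs from the documents.** 15 MORE and 16 TAU participants (Section 1.5); 16 weeks each, target follow-up 80%/75%, benchmark 65%/50% (Section 1.3); 50% of people who begin methadone treatment stop within twelve months (Section 1.2).

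**Assumptions.** Equal true event rates in both arms. Contact declines linearly between visits. One arm is at target and the other at benchmark; the documents do not predict this split.

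**1. Mean weeks in contact** = 8(1 + r8)/2 + 8(r8 + r16)/2.
- Target: 8(1.80)/2 + 8(1.55)/2 = 7.2 + 6.2 = 13.4 weeks, or 13.4/16 = 84%.
- Benchmark: 8(1.65)/2 + 8(1.15)/2 = 6.6 + 4.6 = 11.2 weeks, or 11.2/16 = 70%.

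**2. Same retention in both arms.** The ratio of mean events per participant is 1.00. If nothing is detected after loss, rates are understated by 16% (both at target) or 30% (both at benchmark).

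**3. Different retention.** Let q be the share of events after loss of study contact that clinic staff still report. The ratio is (13.4 + 2.6q)/(11.2 + 4.8q).

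| q | Calculation | Ratio |
|---|---|---|
| 0 | 13.40/11.20 | 1.20 |
| 0.25 | 14.05/12.40 | 1.13 |
| 0.50 | 14.70/13.60 | 1.08 |
| 0.75 | 15.35/14.80 | 1.04 |
| 1 | 16/16 | 1.00 |

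**4. Hypothesis 2 acting through the clinic alone.** Suppose clinics report everything while a person is in treatment and nothing afterwards. With 50% dropout in 52 weeks at constant hazard, h = ln 2/52 and 16h = 0.213. The observed share is (1 − exp(−0.213))/0.213 = 0.90. Even with no dropout at all in MORE the ratio is at most 1/0.90 = 1.11. With half the hazard in MORE the share is 0.95 and the ratio 0.95/0.90, about 1.05. The 50% figure is for people starting treatment, whereas participants must already have 3 months in it (Section 4.2 D).

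**5. Against the noise.** Assume one event per participant per 16 weeks and q = 0. Expected counts are 15 × 0.8375 = 12.6 and 16 × 0.70 = 11.2. The standard error of the log ratio is √(1/12.6 + 1/11.2) = 0.41, against a bias of ln 1.20 = 0.18. In 40,000 simulated trials with a two-sided 5% t-test (level assumed) and MORE as the arm at target, the chance of a significant result against MORE was 3.1%, 4.8%, 6.3% and 7.8% at 0.25, 0.5, 1 and 2 events per 16 weeks. With equal retention it was 2.0% to 2.5%.

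**6. What a rate corrects.** Per observed week the expected ratio is 1.00, but only because equal detection per observed week was assumed. A rate does not correct for the MORE sessions as an extra source. Assume equal retention, other sources detecting a share d of events, and sessions picking up a share s of the rest in 8 of the 16 weeks. The ratio is 1 + 0.5s(1 − d)/d, which is 1.01 for d = 0.9, s = 0.25 and 1.25 for d = 0.5, s = 0.5.

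**7. Duration.** Section 1.10 runs from recruitment in month 4 to the last 16-week follow-up in month 11, which is 8 months inclusive and agrees with its own total. Section 6.3 D gives 12 for the same span.

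**The case against.** A reader might infer that events are seen only while a participant attends study visits, and hence that MORE will look less safe. The documents support neither step. Clinic personnel are asked to report on any participant, in either arm, throughout the study, so a missed assessment does not make someone unseen. The follow-up targets are the same in both arms, and 65%/50% are minimum criteria for success, neither expected losses nor arm-specific. Hypothesis 2 concerns leaving methadone treatment, so it acts mainly through clinic reporting, where step 4 caps the ratio at about 1.11. The list of tests is not exhaustive, the DSMB reviews retention alongside safety each quarter, and this is an unpowered pilot of an intervention described as minimal risk.

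Most of this stands as a limit on size. It does not remove the point. Clinic reporting is passive and needs consent, and it probably weakens once a person leaves treatment, which is the outcome MORE is expected to change. The telephone option appears to be already counted in the benchmarks, because Section 1.9 A allows follow-up by telephone.

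A reader might also infer that event rates will be diluted by the 12-month figure. No planned rate uses it, so the mismatch is one of wording only.

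**Conclusion.** The point holds in conditional form. The safety comparison takes no account of time observed, and its time frames are undefined. Unequal observation is foreseeable but not established. If it occurs, the arm ratio of events per participant could be off by up to about 1.20 in the target-versus-benchmark illustration, and by 1.04 to 1.13 with partial clinic reporting. If it does not occur, the arm ratio is unbiased and only the rates are understated. These figures rest on the assumed retention split, on linear loss between visits and on equal true rates.

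Severity is low to moderate: the bias is small next to chance variation with 31 participants, but the correction is cheap. The conflict between 12 and 8 months is certain and minor.

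**What to change.** **In Section 6.3 G:**
- Define the time frames. Keep the event counts and add the number of participants with at least one event.
- Add person-weeks under observation and events per person-week by arm, for example by Poisson regression with log person-weeks as offset. Section 6.1 A already plans Poisson regression for sessions and dropout.
- Use one stated start point for both arms. Visits are timed from baseline, while randomisation waits until at least 10 people are recruited at a clinic (Section 4.3), so the two dates can differ.
- End each window at the earlier of the week-16 time point and the last date covered by a source available in both arms: assessment, telephone call or clinic record.
- Base the main rate comparison on events from sources common to both arms, and list events known only from MORE sessions separately.
- List every event reported after the last contact. Otherwise a hospitalisation that ended attendance could be dropped.

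**In Sections 6.3 D and 1.10:** reconcile the two durations, also with the one-year study length in Section 1.3 C.

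**Cost:** protocol wording and one derived date per participant. Completed and missed assessments, contact attempts and clinic attendance are already to be recorded. The rates assume that unobserved time resembles observed time, which should be stated beside them.
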